5.13.11 Criteria to Resume Sunitinib or Cabozantinib

Patients may resume treatment with sunitinib or cabozantinib when the drug-related AE(s) resolve to Grade ≤ 1 or baseline value, with the following exceptions:

- Patients may resume dosing in the presence of Grade 2 fatigue.

- Patients who delayed dosing due to 24-hour urine protein ≥ 3.0 g may resume dosing at one dose level reduction when UPCr < 2.0 [< 227 mg/mmol]. Repeat episodes of urine protein ≥ 3 g despite dose reductions require study drug discontinuation (refer to Section 5.14.1.2).
- Patients who delayed dosing due to Grade 3 hypertension may resume dosing at the same dose or at one dose level reduction, at the discretion of the Investigator, when hypertension has improved to Grade ≤ 2 .
- Patients who delayed dosing due to Grade 4 lipase or amylase abnormalities may resume dosing upon resolution to Grade ≤ 2 .
- Patients who develop a pulmonary embolism and/or DVT should have study treatment delayed until therapeutic anticoagulation is established. Treatment with sunitinib may be resumed in patients with pulmonary embolism or DVT if it is determined that the event is uncomplicated and that the patient is deriving clinical benefit from sunitinib treatment and that anticoagulation does not place them at a significant risk that outweighs the benefit of resuming treatment per discretion of the Investigator.
- Patients who delayed dosing due to \leq Grade 2 hemorrhage may resume dosing if bleeding is under control (recovered to at least Grade 1 level) and has a low risk of recurrence.
- Patients who delayed dosing due to major surgery should not resume sunitinib until complete wound healing has taken place. Following sunitinib resumption, patients should be monitored for wound dehiscence, wound infections, and other signs of impaired wound healing.

5.13.12 Sunitinib or Cabozantinib Dose Reduction and Escalation

Table 7 outlines the permitted doses for sunitinib and cabozantinib.

Table 7: Sunitinib and Cabozantinib—Permitted Doses

	Sunitinib	Cabozantinib
0 (starting dose)	50 mg daily	60 mg daily
-1	37.5 mg daily	40 mg daily
-2	25 mg daily	20 mg daily

5.13.12.1 Sunitinib

Sunitinib dose reductions are permitted as per the approved product label for safety reasons or when a concomitant strong cytochrome P450 3A4 (CYP3A4) inhibitor is needed (Appendix 8). Selection of an alternative concomitant medication with minimal or no enzyme inhibition potential is recommended whenever possible.

After toxicity requiring a dose delay has improved and meets the criteria to resume dosing (Section 5.13.11), patients should resume sunitinib at one dose level reduction. Dose reductions

should occur in 12.5 mg decrements. No more than 2 dose reductions are allowed. If more than two dose reductions are necessary (i.e., reduction to less than 25 mg daily), the patient must be permanently discontinued (Section 5.14.1.2).

Patients who required a dose delay due to Grade 3 hypertension, which improved with antihypertensive medications, or any Grade 2 or 3 drug-related adverse event or asymptomatic laboratory abnormality that improved to Grade \leq 1 within 7 days with supportive medical care may resume sunitinib at the same dose or a reduced dose, at the discretion of the Investigator.

Patients who required a dose delay due to 24-hour urine protein \geq 3 g, may resume study treatment at a reduced dose once UPCR is $<$ 2 ($<$ 227 mg/mmol). Repeat episodes of urine protein \geq 3 g despite dose reductions require study drug discontinuation (refer to Section 5.14.1.2).

At the time a dose reduction is considered, also refer to Section 5.13.10 for dose delay recommendations and Section 5.14 for discontinuation criteria.

Sunitinib dose re-escalations are permitted as per the approved product label when a concomitant CYP3A4 inducer is needed (Appendix 8); however, escalation above the starting dose is not allowed. Selection of an alternative concomitant medication with minimal or no enzyme induction potential is recommended whenever possible.

5.13.12.2 Cabozantinib

Reduce the starting dose of cabozantinib to 40 mg once daily in patients with moderate hepatic impairment (i.e., Child-Pugh Class B); refer to the cabozantinib (Cabometyx[®]) US Prescribing Information and/or the corresponding SmPC for updated dosing guidance or further information. For patients receiving a concomitant strong CYP3A4 inducer or inhibitor, follow the dosing guidelines in the Package Insert, SmPC, or local health authority guidelines applicable to your country.

Dose reductions for adverse event management are allowed for cabozantinib (Table 7). Cabozantinib doses will not be re-escalated once reduced, unless a concomitant strong CYP3A4 inducer is started (see Section 5.13.12.3); however, escalation above the starting dose is not allowed.

After toxicity requiring a dose delay has improved and meets the criteria to resume dosing (Section 5.13.11), patients who were receiving cabozantinib 40 mg daily prior to the delay will resume cabozantinib at 20 mg daily. If more than 2 dose reductions are necessary (i.e., reduction to less than 20 mg daily) or more than 1 dose reduction in patients with Child-Pugh Class B (i.e., starting dose 40 mg daily), cabozantinib must be permanently discontinued (Section 5.14.1.3).

Patients who required a dose delay due to 24-hour urine protein ≥ 3 g, may resume study treatment at a reduced dose once UPCr is < 2 [< 227 mg/mmol]. Recurrent 24-hour urine protein ≥ 3 g after dose reduction requires study drug discontinuation (refer to Section 5.14.1.3).

Patients who required a dose delay due to Grade 3 hypertension, which improved with antihypertensive medications, or any Grade 2 or 3 drug-related adverse event or asymptomatic laboratory abnormality that improved to Grade ≤ 1 within 7 days with supportive medical care may resume cabozantinib at the same dose or a reduced dose, at the discretion of the Investigator.

Patients with asymptomatic Grade 2 drug-related AST, ALT or total bilirubin elevation, or Grade 3 drug-related lipase or amylase abnormalities that are not associated with symptoms or clinical manifestations of pancreatitis may reduce cabozantinib by 1 dose level, without delaying dosing, at the discretion of the Investigator.

5.13.12.3 For Patients Who Start Taking a Concomitant Strong CYP3A4 Inhibitor

Reduce the daily dose of cabozantinib or sunitinib by one dose level. Resume the dose that was used prior to initiating the CYP3A4 inhibitor 2 to 3 days after discontinuation of the strong inhibitor (see Prescribing Information for cabozantinib and sunitinib).

5.14 Discontinuation Criteria

5.14.1 Discontinuation from Study Treatment

Patients MUST discontinue investigational product (and non-investigational product at the discretion of the Investigator) for any of the following reasons:

- Patient's request to stop study treatment. Patients who request to discontinue study treatment will remain in the study and must continue to be followed for protocol specified follow-up procedures. The only exception to this is when a patient specifically withdraws consent for further assessments or contact with him/her or persons previously authorized by patient to provide this information.
- 2 years since Cycle 1 Day 1 (Arm A only)
- Any clinical AE, laboratory abnormality, or intercurrent illness which, in the opinion of the Investigator, indicates that continued participation in the study is not in the best interest of the patient
- See additional study treatment discontinuation criteria specific to NKTR-214 and nivolumab (Section 5.14.1.1), sunitinib (Section 5.14.1.2), and cabozantinib (Section 5.14.1.3) due to AEs.
- Termination of the study by the Sponsor

- Loss of ability to freely provide consent through imprisonment or involuntarily incarceration for treatment of either a psychiatric or physical (e.g., infectious disease) illness. (Note: Under specific circumstances, a patient who has been imprisoned may be permitted to continue as a patient. Strict conditions apply and Sponsor approval is required.)
- Disease progression in the absence of clinical benefit as determined by the Investigator
- Occurrence of a clinically significant AE found to be unacceptable or nonresolution of a clinically significant AE for > 8 weeks
- Symptomatic deterioration in the absence of tumor progression per mRECIST 1.1.
- Noncompliance of the patient with protocol-mandated procedures based on the judgment and agreement of both the Investigator and Sponsor

If a patient has not progressed following discontinuation of study drug(s), every effort should be made to continue to obtain radiographic tumor assessments (until the patient has documented progression by both the BICR and Investigator's assessment or begins a subsequent anticancer therapy).

A patient may also be withdrawn from investigational product/study by the Sponsor, Regulatory Authorities, or IRBs/IECs.

Patients may choose to discontinue the study at any time, for any reason, and without prejudice to further treatment.

Refer to the Schedule of Events ([Table 4](#)) for data to be collected at the time of treatment discontinuation and follow-up and for any further evaluations that can be completed.

If a female patient becomes pregnant, administration of the study drug(s) must be discontinued immediately, and the Investigator must notify the Sponsor within 24 hours of awareness of the pregnancy. Refer to [Section 8.12.2](#) (Pregnancy).

All patients who discontinue study treatment should comply with protocol specified follow-up procedures as outlined in [Table 4](#). The only exception to this requirement is when a patient withdraws consent for all study procedures including post-treatment study follow-up or loses the ability to consent freely (i.e., is imprisoned or involuntarily incarcerated for the treatment of either a psychiatric or physical illness).

If study treatment is discontinued prior to the patient's completion of the study, the reason for the discontinuation must be documented in the patient's medical records and entered on the appropriate CRF page.

5.14.1.1 NKTR-214 Combined with Nivolumab Discontinuation Criteria

Patients meeting any of the following criteria will be required to permanently discontinue all assigned study drug(s). However, per Investigator assessment, NKTR-214 or nivolumab may be

continued as a monotherapy if the toxicities listed below are considered related to only one of the study drugs, once the criteria to resume are met (Section 5.13.7). For CVA events and suspected TIA events, follow the criteria described below (additional details are provided in the CVA management algorithm in [Appendix 6](#)).

NKTR-214 combined with nivolumab treatment should be permanently discontinued for the following:

- Any \geq Grade 2 drug-related uveitis, eye pain or blurred vision that does not respond to topical therapy and does not improve to Grade 1 severity within the retreatment period OR requires systemic treatment
- Grade 3 or 4 infusion reaction of any duration that occurs during the:
 - NKTR-214 infusion or prior to the nivolumab infusion requires discontinuation of NKTR-214.
 - Nivolumab infusion or later requires discontinuation of both NKTR-214 and nivolumab.
- Any Grade 3 non-skin, drug-related AE lasting > 7 days or recurs, with the following exceptions for laboratory abnormalities, drug-related uveitis, pneumonitis, bronchospasm, neurologic toxicity, hypersensitivity reactions, and endocrinopathies
 - Grade 3 drug-related uveitis, pneumonitis, bronchospasm, neurologic toxicity, myocarditis, or hypersensitivity reaction of any duration requires discontinuation
 - Grade 3 drug-related endocrinopathies (excluding adrenal insufficiency) adequately controlled with only physiologic hormone replacement do not require discontinuation.
 - Note: For adrenal insufficiency of Grade ≥ 3 , treatment needs to be discontinued regardless of control with hormone replacement (hospitalization for diagnostic workup of adrenal insufficiency without severe symptoms should not require discontinuation).
 - Grade 3 drug-related laboratory abnormalities do not require treatment discontinuation except:
 - Grade 3 drug-related thrombocytopenia > 7 days or associated with bleeding requires discontinuation
 - Any drug-related LFT abnormality that meets the following criteria require discontinuation (also see Hepatic Adverse Event Management Algorithm, in nivolumab Investigator's Brochure):
 - ◆ Treatment-emergent ALT or AST > 3 times ULN ($> 2 \times$ baseline AND $> 3 \times$ ULN for patients with baseline elevation) AND
 - ◆ Total bilirubin > 2 times ULN ($> 2 \times$ baseline AND $> 2 \times$ ULN for patients with baseline elevation) or clinical jaundice, without initial findings of cholestasis (e.g., elevated serum alkaline phosphatase) (see Section 8.10)

In most cases of Grade 3 AST or ALT elevation that do not improve with hepatic AE management, study treatment will be permanently discontinued (see Section 5.13 for more details). If the Investigator determines a possible favorable benefit/risk ratio that warrants continuation of study treatment, a discussion between the Investigator and the Medical Monitor must occur. For IL-2 mediated ALT/AST elevations $< 8.0 \times \text{ULN}$ in Cycle 1 only, study treatment does not need to be discontinued.

- Any Grade 4 drug-related adverse event or laboratory abnormality (including but not limited to creatinine, AST, ALT, or total bilirubin), except for the following events which do not require discontinuation:
 - Grade 4 neutropenia ≤ 7 days
 - Grade 4 lymphopenia or leukopenia or asymptomatic amylase or lipase
 - Isolated Grade 4 electrolyte imbalances/abnormalities that are not associated with clinical sequelae and are corrected with supplementation/appropriate management within 72 hours of their onset
 - Grade 4 drug-related endocrinopathy adverse events (except adrenal insufficiency or hypophysitis), such as, hyper- or hypothyroidism, or glucose intolerance, which resolve or are adequately controlled with physiologic hormone replacement (corticosteroids, thyroid hormones) or glucose-controlling agents, respectively, may not require discontinuation after discussion with and approval from the Medical Monitor.
 - Note: For Grade ≥ 3 adrenal insufficiency and/or Grade ≥ 4 hypophysitis, treatment needs to be discontinued regardless of control with hormone replacement (hospitalization for diagnostic workup of adrenal insufficiency without severe symptoms should not require discontinuation).
- Any event that leads to delay in dosing lasting > 8 weeks from the previous dose requires discontinuation, with the following exceptions:
 - Dosing delays to allow for prolonged steroid tapers to manage drug-related adverse events are allowed. Prior to re-initiating treatment in a patient with a dosing delay lasting > 8 weeks, the Medical Monitor must be consulted and agree with the rationale for resuming therapy. Tumor assessments should continue as per protocol even if dosing is delayed. Periodic study visits to assess safety and laboratory studies should also continue every 3 weeks or more frequently if clinically indicated during such dosing delays.
- Any adverse event, laboratory abnormality, or intercurrent illness which, in the judgment of the Investigator, presents a substantial clinical risk to the patient with continued nivolumab dosing.
- Any new CVA event confirmed by imaging (diffusion-weighted imaging [DWI] MRI preferred unless contraindicated), regardless of neurological symptoms, and for suspected TIA without clear alternative etiology (see [Appendix 6](#)).

5.14.1.2 Sunitinib Discontinuation Criteria

Treatment with sunitinib should be permanently discontinued for any of the following:

- Any requirement for more than 2 sunitinib dose reductions
- Any Grade drug-related arterial thrombosis
- Grade ≥ 3 drug-related hemorrhage or recurrent Grade 3 drug-related hemorrhage after dose reduction
- Grade 4 drug-related symptomatic venous thrombosis
- LVEF reduction $\geq 50\%$ from baseline
- Grade 4 drug-related cardiac toxicity
- Any other Grade ≥ 2 drug-related arterial or venous thromboembolic events including cerebrovascular ischemia, cardiac ischemia, or peripheral or visceral arterial ischemia
- Erythema multiforme, Stevens-Johnson syndrome, toxic epidermal necrolysis or necrotizing fasciitis
- Thrombotic microangiopathy
- Nephrotic syndrome or repeat episodes of urine protein ≥ 3 g despite dose reductions
- Angioedema due to hypersensitivity
- Two or more symptomatic episodes of hypertension despite modification of antihypertensive medication(s) and reduction of sunitinib dose
- Any drug-related LFT abnormality that meets the following criteria require discontinuation:
 - Treatment-emergent ALT or AST > 3 times ULN ($> 2 \times$ baseline AND $> 3 \times$ ULN for patients with baseline elevation)
 - Total bilirubin > 2 times ULN ($> 2 \times$ baseline AND $> 2 \times$ ULN for patients with baseline elevation) or clinical jaundice, without initial findings of cholestasis (e.g., elevated serum alkaline phosphatase) (see Section 8.10)
 - Sunitinib should be interrupted for Grade 3 or 4 drug-related hepatic adverse reactions and discontinued if there is no resolution within 7 days. Sunitinib should be permanently discontinued if a patient subsequently experiences Grade 3 or 4 changes in LFT or have other signs and symptoms of liver failure.
- Any dosing delay lasting > 8 weeks unless the Medical Monitor is consulted and agrees with the rationale for resuming therapy after a delay > 8 weeks. Note that tumor assessments should continue as per protocol even if dosing is delayed.
- Any adverse event, laboratory abnormality, or intercurrent illness which, in the judgment of the Investigator, presents a substantial clinical risk to the patient with continued sunitinib dosing.

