5.13.10 Sunitinib or Cabozantinib Dosing-Delay Criteria

Sunitinib or cabozantinib dosing should be delayed for the following:

- If UPCR ≥ 2.0 [≥ 227 mg/mmol] urine dipstick protein $\geq 3+$, obtain 24-hour urine protein to determine if dosing should be delayed.
 - Dosing may proceed if 24-hour urine protein < 3 g.
 - Delay dosing if 24-hour urine protein ≥ 3 g (see Section 5.13.11 for criteria to resume).
 - Recurrent 24-hour urine protein ≥ 3 g after dose reduction requires study drug discontinuation (refer to Sections 5.14.1.2 and 5.14.1.3).
- Clinical manifestations of CHF
- LVEF $> 20\%$ but $< 50\%$ below baseline
- Any Grade 2 drug-related hemorrhage
- Any Grade 2 or 3 drug-related venous thrombosis requiring anticoagulation, with the following exception:
 - Any recurrent or worsening venous thromboembolic event after restarting sunitinib or cabozantinib will require discontinuation
- Any Grade 3 drug-related adverse event or Grade 3 drug-related laboratory abnormality (e.g., AST, ALT, total bilirubin) that persists for more than 1 week or worsens despite supportive care management, with the following exceptions:
 - Grade ≥ 2 drug-related arterial thromboembolic events, including cerebrovascular ischemia, cardiac ischemia, or peripheral or visceral arterial ischemia, require discontinuation.
 - Grade ≥ 3 drug-related hemorrhage requires discontinuation (Section 5.14.1.2).
 - Drug-related AST or ALT $> 8 \times$ ULN requires discontinuation (Section 5.14.1.2).

- Concurrent AST or ALT $> 3 \times$ ULN ($> 2 \times$ baseline AND $> 3 \times$ ULN for patients with baseline elevation) and total bilirubin $> 2 \times$ ULN ($> 2 \times$ baseline AND $> 2 \times$ ULN for patients with baseline elevation), consistent with potential drug-induced liver injury (see Section 8.10), requires discontinuation.
- Grade 3 drug-related amylase or lipase abnormalities that are not associated with symptoms or clinical manifestations of pancreatitis do not require dose delay. In such cases, more frequent monitoring (e.g., weekly) of amylase and lipase is recommended. If amylase or lipase worsens to Grade 4 severity or the patient develops symptoms or clinical manifestations of pancreatitis, dosing should be delayed.

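### For a first drug-related Grade 2–3 venous thrombosis requiring anticoagulation on a control-arm TKI, Protocol 5.13.10 and 5.13.11 foresee restart (expressly for sunitinib), while 5.14.1.2 and 5.14.1.3 require permanent discontinuation

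*Protocol*

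**What the plan says.** Four Protocol sections bear on the same event in Arm B.

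- **5.13.10 (delay, both TKIs).** Dosing is delayed for "Any Grade 2 or 3 drug-related venous thrombosis requiring anticoagulation, with the following exception". The exception reads "Any recurrent or worsening venous thromboembolic event after restarting sunitinib or cabozantinib will require discontinuation". A separate stop rule in the same section, at Grade 2 or higher, is confined to "drug-related arterial thromboembolic events, including cerebrovascular ischemia, cardiac ischemia, or peripheral or visceral arterial ischemia, require discontinuation".
- **5.13.11 (resume, both TKIs).** The general rule begins "Patients may resume treatment with sunitinib or cabozantinib when the drug-related AE(s) resolve to Grade" and is followed by a list of exceptions. One of them says "Patients who develop a pulmonary embolism and/or DVT should have study treatment delayed until therapeutic anticoagulation is established". It continues "Treatment with sunitinib may be resumed in patients with pulmonary embolism or DVT if it is determined that the event is uncomplicated", and adds that the patient must be benefiting and that "anticoagulation does not place them at a significant risk that outweighs the benefit of resuming treatment per discretion of the Investigator".
- **5.14.1.2 (permanent discontinuation, sunitinib).** The list has one bullet for arterial thrombosis of any grade and one for symptomatic Grade 4 venous thrombosis. A catch-all at Grade 2 or higher then covers other "drug-related arterial or venous thromboembolic events including cerebrovascular ischemia, cardiac ischemia, or peripheral or visceral arterial ischemia".
- **5.14.1.3 (permanent discontinuation, cabozantinib).** The same catch-all appears. The bullet before it covers myocardial infarction and cerebrovascular events only.

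The introduction to 5.13 makes the discontinuation criteria in 5.14 mandatory.

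**The concern.** A patient on control therapy develops a first drug-related DVT of Grade 2 or 3 and is anticoagulated. A site that works from the delay and resume sections will hold the drug and consider restarting it. A site that works from the discontinuation lists will stop it for good.

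This is a serious toxicity, and the two readings carry opposite risks. One re-exposes the patient to a drug that the protocol says to stop. The other ends control therapy that the resume section would allow.

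Deviation handling is also touched. SAP 7.2 counts as an important deviation a patient who meets withdrawal criteria but is not withdrawn. A patient restarted in good faith under 5.13.11 could be recorded that way, subject to the manual review and the study-team decision that SAP 7.2 provides for.

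**Working it through.** No arithmetic on the trial's operating characteristics applies. The check sets the rules side by side for one event: a first, drug-related venous thrombosis of Grade 2 or 3 requiring anticoagulation, presenting as PE or DVT.

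| Section | Sunitinib | Cabozantinib |
|---|---|---|
| 5.13.10 | Delay; stop only on recurrence or worsening after restart | Same |
| 5.13.11, PE/DVT bullet | Delay until anticoagulated; may then resume, on conditions | Delay until anticoagulated; no restart sentence |
| 5.14.1.2 / 5.14.1.3 | Permanent stop | Permanent stop |

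**Step 1: does the catch-all reach this event?** Yes. It names venous events, starts at Grade 2, requires drug-relatedness, and makes no exception for a first, uncomplicated or anticoagulated event.

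**Step 2: is restart permitted elsewhere?** For sunitinib, expressly, in 5.13.11. For cabozantinib, only 5.13.10 points that way: it orders a delay rather than a stop, and its exception speaks of events after either drug has been restarted.

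**Step 3: which grades?** Two drugs by three grades (2, 3, 4) give 6 combinations.
- Grades 2 and 3 conflict for both drugs: 2 × 2 = 4. Two of these (sunitinib) involve an express permission; the other two (cabozantinib) rest on 5.13.10 against 5.14.1.3.
- The two Grade 4 combinations agree. The 5.13.10 delay bullet ends at Grade 3, both 5.14 lists stop treatment, and a life-threatening PE could hardly count as uncomplicated under 5.13.11.

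These are counts of rules, not of patients.

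**Step 4: does precedence dissolve the conflict?** Suppose 5.14 always prevails. The 5.13.10 venous bullet concerns, by its own terms, drug-related events of Grade 2 or 3. All of these would already have been stopped, so the bullet and its after-restart exception would never operate. The PE/DVT bullet in 5.13.11 would keep a role only for events that are not drug-related, but its text does not say so.

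**Step 5: do cross-references help?** Where 5.13.10 means 5.14 to govern, it often says so: for hemorrhage, for transaminases above 8 × ULN and for recurrent proteinuria. The venous bullet cites nothing. The Arm A resume section (5.13.7) excludes patients who meet permanent-discontinuation criteria; 5.13.11 contains no such general exclusion.

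**The case against.** **Precedence is stated.** Section 5.13 makes the 5.14 criteria mandatory, and restart is only ever permitted, never required. Permanent discontinuation therefore complies with every section. This stands: a reader might infer that sites have no compliant course, and that would be wrong. But it shows only which course is safe. The permission in 5.13.11 remains in print, and a site that uses it breaches 5.14.1.2.

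**The catch-all may mean other kinds of event.** In 5.14.1.2, arterial thrombosis of any grade and symptomatic Grade 4 venous thrombosis have their own bullets, and the catch-all's examples are all ischemic. On that view, Grade 2–3 venous thrombosis on sunitinib falls outside it. The reading is possible but strained. The catch-all names venous thromboembolic events, and 5.13.10 itself uses that term for the recurrence of a venous thrombosis. Drug-related PE would still be caught by the catch-all although 5.13.11 allows restart after it. The reading is not available for cabozantinib, where no venous event is listed earlier.

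**Cabozantinib.** A reader might infer that cabozantinib may resume after PE or DVT under the general rule in 5.13.11, which names both drugs. The text does not support this. The PE/DVT bullet is an exception to that rule, and its restart sentence names sunitinib alone. Section 5.13.12.2 does not supply the permission either: it reads as setting the dose for a patient already eligible to resume. This part of the objection stands and narrows the cabozantinib conflict to 5.13.10 against 5.14.1.3.

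**Materiality.** No incidence is given, and restart is hedged by several conditions. Both points are fair, and they limit the weight of the finding.

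**Conclusion.** Wrong as written. For a first drug-related Grade 2–3 venous thrombosis requiring anticoagulation, the protocol delays both TKIs with restart in view and also lists the event as a mandatory reason to stop permanently. The contradiction is express for sunitinib. For cabozantinib it is real but rests on less text.

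The conclusion assumes that *other* in the catch-all does not remove Grade 2–3 venous events, which is the more natural reading. It does not extend to venous events that are not drug-related or do not require anticoagulation.

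The effect is confined to Arm B safety management and deviation handling. A reader might infer that differing control-arm exposure disturbs the primary comparisons. The documents do not support that: alpha and power do not depend on these rules, ORR and OS are analysed as randomized (Protocol 9.3), and scans and survival follow-up continue after treatment stops (Protocol 5.6 and 5.6.2). No number of affected patients can be derived.

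**What to change.** **If 5.14 is meant to govern, as 5.13 states:**
- In 5.13.10, delete the Grade 2–3 venous delay bullet and its after-restart exception, and add drug-related venous events of Grade 2 or higher to the existing arterial discontinuation line.
- In 5.13.11, limit the PE/DVT bullet to events that are not drug-related.
- Leave 5.14.1.2 and 5.14.1.3 unchanged.

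**If the sponsor intends restart:**
- In 5.14.1.2 and 5.14.1.3, add to the catch-all an exception for a first Grade 2–3 venous event requiring anticoagulation and managed under 5.13.10 and 5.13.11.
- Add recurrent or worsening venous events after restart as a stop criterion in both lists.
- In 5.13.11, state whether cabozantinib may resume.

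Under this second course, simply striking the venous wording from the catch-all would go too far. It would also remove the present stop for Grade 2–3 venous events that do not require anticoagulation, and would leave non-symptomatic Grade 4 venous events on sunitinib uncovered.

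The clinical choice belongs to the sponsor. The cost is protocol wording in two sections for the first course or three for the second, with no change to sample size, alpha or analyses.
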